3. STUDY ENDPOINTS

3.1. Primary Effectiveness Analysis

The primary endpoint is time to first FACE (cardiac, renal, or cerebrovascular events) ") since start of treatment for migalastat and or ERT and from time of diagnosis for untreated with particular focus on the added value of the recent addition of migalastat as a treatment option. A formal statistical analysis will be using the initial treatment cohort. Descriptive statistics will be calculated since each start of treatment (after each switch).

FACEs are defined as the following:

- Cardiac clinical events:
 - Myocardial infarction
 - New symptomatic arrhythmia requiring medication, direct current cardioversion, or interventional procedure (e.g., ablation, pacemaker, or defibrillator implantation)
 - Unstable angina defined by national practice guidelines and accompanied by electrocardiographic changes and non-ST segment elevation myocardial infarction [UA/NSTEMI]) and accompanied by electrocardiographic changes
 - Congestive heart failure requiring hospitalization
 - Any major cardiac medical procedure (e.g., valve replacement, stent-implantation, transplant, or persistent atrial fibrillation)
- Cerebrovascular clinical events:
 - Stroke (documented by a physician)
 - Transient ischemic attack (documented by a physician)
- Renal clinical events
 - Doubling of serum creatinine level from the start of analysis (2 consecutive values)
 - End-stage renal disease (ESRD) requiring long-term dialysis or transplantation
- Death due to FACEs

All FACEs will be analyzed together as a composite and separately in each category (cardiac, cerebrovascular, and renal). Death due to FACE will be analyzed under the category in which it occurred (cardiac, cerebrovascular, or renal).

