13.2. Secondary Endpoint: Prevalence of FACEs

Treatment Switch

The first analysis will address events that occur on therapy from the Analysis Start Date up until 30 days after the patient stops therapy or from the switch date to the date of a subsequent switch or stopping therapy. The second analysis will address events that occur on therapy from the Analysis Start Date up until the patient stops therapy or switches therapy or from the switch date to the date of a subsequent switch or stopping therapy.

Analysis Method

The prevalence of FACEs is calculated as a ratio of patients with at least one FACE on a given therapy divided by the number of patients on that therapy. If a patient starts dialysis or receives a kidney or heart transplant, the events afterwards will be excluded.

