13.3. Secondary Endpoint: Incidence of FACEs

As this is an observational study, patients may switch or stop therapies. If a patient starts dialysis or receives a kidney or heart transplant, the events afterwards will be excluded.

The analysis of the incidence rate (number of patients with at least 1 event per 1000 person-years) will be performed on the Primary and Secondary Effectiveness Populations.

Treatment Switch

The analysis will address events that occur on migalastat or ERT therapy from the Analysis Start Date or switch date up until 30 days after the patient stops therapy or switches therapy. For the patients untreated at enrollment to the study, the analysis will address events from the time of diagnosis until the patient starts a therapy or during periods that they are untreated after a switch.

The second analysis will address events that occur on migalastat or ERT therapy from the Analysis Start Date or switch date. For the patients untreated at enrollment to the study, the analysis will address events from the time of diagnosis until the patient starts a therapy or during periods that they are untreated after a switch.

Analysis Methods

The calculation of the incidence rate (number of events per 1000 person-years) will be performed on the Primary and Secondary Effectiveness Populations.

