13.9. Secondary Endpoint: Prevalence and Incidence of micro – or Macroalbuminuria

The prevalence and incidence of micro (> 30 mg/g creatinine) or macroalbuminuria (> 300) by urinary albumin/creatinine ratio (ACR) or urinary 24 h protein excretion from each baseline (diagnosis, and start of treatment) to compare between migalastat-treated, ERT-treated patients and untreated patients will be analyzed using same methodology as for incidence and prevalence of FACEs.

Analysis by ACR categories will be performed if enough data are available.

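### Albuminuria incidence (SAP 13.9) has no at-risk set: patients already above the cut-off when a treatment period starts are not removed, so the rate does not measure onset

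*SAP*

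**What the plan says.** SAP 13.9 (listed in SAP 3.2 and in the protocol's secondary endpoints) asks for prevalence and incidence of micro- and macroalbuminuria "by urinary albumin/creatinine ratio (ACR) or urinary 24 h protein excretion from each baseline (diagnosis, and start of treatment"), in migalastat-treated, ERT-treated and untreated patients. On method it says only that "untreated patients will be analyzed using same methodology as for incidence and prevalence of FACEs".

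The borrowed rules are these.

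- **Incidence numerator, SAP 13.3.** Two versions stand in the same section: "The analysis of the incidence rate (number of patients with at least 1 event per 1000 person-years") and "The calculation of the incidence rate (number of events per 1000 person-years").
- **Start of counting, SAP 13.3.** Counting restarts at a switch: "The second analysis will address events that occur on migalastat or ERT therapy from the Analysis Start Date or switch date". Untreated periods that follow a switch are also included. The first analysis in that section adds a 30-day carry-over after stopping or switching.
- **Exclusions, SAP 13.3.** There is one: "If a patient starts dialysis or receives a kidney or heart transplant, the events afterwards will be excluded". Status at the start of the period is not mentioned.
- **Prevalence, SAP 13.2.** A "ratio of patients with at least one FACE on a given therapy divided by the number of patients on that therapy".

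SAP 7.3 has a general reporting rule under which exposure-adjusted incidence rates count patients who have a new event. It does not say what makes a laboratory state new.

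**The concern.** Most FACEs, such as stroke or infarction, are dated occurrences, and counting patients with at least one during a treatment period is a workable incidence measure. ACR above a cut-off is different. It is a state, read at yearly or two-yearly visits (protocol, Study design and Method), and it can persist through a change of therapy. An incidence rate for a state needs two definitions that 13.9 and 13.3 do not supply: who is at risk when the period begins, and what counts as onset.

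Without them the rate reflects how many patients entered each period already positive. The endpoint compares three treatment groups at an unadjusted two-sided 0.05 level for any test made (SAP 3.2), in about 115 patients (SAP 4), so a few carried-over cases could dominate a group's rate. The missing definitions could also be settled after the data are seen.

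**Working it through.** The documents state no albuminuria rate, baseline prevalence, event count or period length, so there is no figure to reproduce. The check is a reading of the rules, followed by an illustration with assumed inputs.

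**Reading the rules.** Take a patient with ACR above 30 mg/g from diagnosis onward who passes through an untreated, an ERT and a migalastat period. Under the literal 13.3 count the patient has at least one positive value in each period, and nothing in 13.3 or 13.9 removes any of them. That is three counted cases and no onset during follow-up. The incidence numerator then holds essentially the same patients as the prevalence numerator of 13.2.

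**Formulas.** Let *p* be the proportion positive at period start, λ a constant onset rate, *T* the period length and *N* the patients per group. The state is assumed to persist.

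- Onsets: *N*(1−*p*)(1−e^(−λ*T*))
- Literal rate: (*Np* + onsets) / (*NT*)
- Numerator-only rate (7.3 applied, denominator untouched): onsets / (*NT*)
- At-risk rate: onsets / person-years of initially negative patients up to onset, which equals λ

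**Unequal periods, equal prevalence** (assumed: *N* = 30, *p* = 40%, λ = 20 per 1000 person-years in both groups, *T* = 5 versus 15 years). There are 12 positive and 18 at risk at the start.

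- Onsets: 18(1−e^(−0.1)) = 1.71 and 18(1−e^(−0.3)) = 4.67
- Literal: (12+1.71)/150 = 91.4 and (12+4.67)/450 = 37.0 per 1000; ratio 2.47
- Literal count, person-time of initially negative patients stopped at onset and none for the others: 13.71/85.6 = 160 and 16.67/233 = 71.5; ratio 2.24
- At-risk: 1.71/85.6 and 4.67/233, both 20.0; ratio 1.00
- With *p* = 10%, literal: (3+27×0.0952)/150 = 37.1 and (3+27×0.2592)/450 = 22.2; ratio 1.67

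Over a wider range (4 versus 12 years, *p* = 20% to 60%, onset 20 or 40 per 1000), the literal ratio runs from 1.89 to 2.76. At *p* = 0 it is 1.08 or 1.16.

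**Equal periods, unequal prevalence** (*T* = 6 years, λ = 20 per 1000, *p* = 50% versus 20%; 1−e^(−0.12) = 0.1131).

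- Literal: (0.5+0.5×0.1131)/6 = 92.8 and (0.2+0.8×0.1131)/6 = 48.4 per 1000; ratio 1.92
- Numerator-only: 0.5×0.1131/6 = 9.4 and 0.8×0.1131/6 = 15.1; ratio 0.5/0.8 = 0.63

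The two readings move the same comparison in opposite directions, and the true ratio is 1.00.

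**Numerator-only level.** At *T* = 6 years a true 20 becomes 15.1, 11.3 and 7.5 per 1000 for *p* = 20%, 40% and 60%. Part of the shortfall arises because person-time runs on after onset (18.8 at *p* = 0). The rest is the factor 1−*p*. Period length matters little under this reading (ratio 1.08 for 4 versus 12 years at onset 20).

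**The case against.** The strongest reply is SAP 7.3. Its reference to new events, together with 13.9 asking for prevalence and incidence as separate quantities, would let a programmer drop baseline-positive patients from the incidence numerator. This stands against one tempting inference, that the plan counts a persisting state as a fresh case in every treatment period. No passage says so. It follows only from a literal reading of 13.3. But 7.3 does not repair the analysis: *new* could mean new to the period or new ever, and nothing takes the baseline-positive person-time out of the denominator.

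A reader might also infer that migalastat would be made to look harmful, since it became available in 2016 (protocol, Rationale and background) and would have shorter periods. The documents do not support a direction. They give no group sizes, period lengths, treatment sequences or baseline prevalence, and the two readings can pull opposite ways.

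A third inference is that one raised value is accepted as onset, in conflict with the renal FACE, which requires "Doubling of serum creatinine level from the start of analysis (2 consecutive values"). Section 13.9 is silent on confirmation; it does not adopt a single-value rule. The creatinine rule and the sustained decline of 13.8 do not bind it. With visits one or two years apart, requiring confirmation is a trade-off.

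Two further points are fair. Some FACEs (ESRD, persistent atrial fibrillation) are also lasting states, so the gap begins in 13.3. And SAP 15.6 analyses urine albumin and ACR longitudinally, with possible shift tables from the Analysis Start Date. That gives some protection for interpretation but leaves the incidence endpoint undefined.

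**Conclusion.** The point holds as an undefined at-risk set and onset rule for a secondary endpoint. Under either available reading the rate is not the onset rate. It depends on baseline prevalence, and under the literal reading strongly on period length as well.

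The size and direction of any between-group bias cannot be fixed from the documents. Under the assumed inputs above, the literal reading gives a rate ratio of about 2.5 (5 versus 15 years, 40% positive) or about 1.7 (10% positive) where the truth is 1.0. The numerator-only reading gives 11.3 against a true 20 per 1000 person-years (40% positive, 6 years). These figures show that the effect can be large; they are not estimates for this cohort. The plan should be corrected before analysis, but the primary endpoint is not affected.

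**What to change.** Give SAP 13.9 its own incidence rule in place of the cross-reference.

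- **At-risk set.** For each period, compute incidence of microalbuminuria only in patients with ACR at or below 30 mg/g at that period's baseline, and of macroalbuminuria only in those at or below 300. Remove baseline-positive patients from numerator and denominator.
- **Baseline value.** State which value is used. SAP 11.1 takes the assessment closest to diagnosis, which may fall after it. SAP 11.2 admits only values obtained on the treatment, so the baseline could be post-start. An at-risk flag needs a stated exception to these rules or a stated justification for keeping them.
- **Onset.** Count only the first crossing in a period, stop person-time there, and assign each value to one period so that the 30-day carry-over cannot count it twice.
- **Prevalence.** Report baseline-positive patients separately, as prevalence at period start by therapy.
- **24 h protein.** Section 13.9 states its cut-offs in ACR terms only. If 24 h protein can establish status, its cut-off must be stated.

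A confirmed-onset definition (2 consecutive values) can be added as an optional sensitivity analysis.

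The cost is SAP wording and a flag derived from ACR values already collected. The incidence analysis will have fewer patients and events, and patients without a usable baseline ACR drop out. A patient whose albuminuria remits and returns after a switch would count again, so the rate should be labelled as onset within a period, not first-ever onset.

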2. OVERVIEW OF STUDY DESIGN

This is a retrospective study of prospectively collected patient data with the use of secondary patient data from both paper and electronic patient files. All patients are treatment naïve at time of diagnosis. Both migalastat and ERT will be studied retrospectively. Also untreated patients will be studied by assessment of relevant clinical and laboratory variables. The analysis will originate at the time of diagnosis.

The patients have been followed for more than 20 years from 2001 until December 2023. All identified patients with Fabry disease, whether receiving specific Fabry medication or not, have been offered annual or biannual thorough workups including examinations of Fabry associated organ function and symptoms. The study will be carried out at the Danish National Fabry Centre, Department of Endocrinology, Copenhagen University Hospital.

All patients from the Danish National Fabry Centre will be included. Subgrouping is aimed at depending on available numbers: non-amenable, amenable, classic, non-classic, males, females, treated including type of treatment or untreated.

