7. STATISTICAL ANALYSIS CONSIDERATIONS

7.1. Conventions

Unless otherwise noted, data will be summarized in tabular format by treatment groups (ie, migalastat-treated, ERT-treated, and untreated patients where appropriate). Enrollment summaries will also include a total summary column.

The precision of original measurements will be maintained in summaries, when possible. Means, medians, and standard deviations will be presented with an increased level of precision; means and medians will be presented to 1 more decimal place than the raw data, and the standard deviations will be presented to 2 more decimal places than the raw data.

Summaries of continuous variables that have some values recorded using approximate values (eg, < or >) will use imputed values. The approximate values will be imputed using the closest exact value for that measurement. For tables where rounding is required, rounding will be done to the nearest round-off unit. For example, if the round-off unit is the ones place (ie, integers), values \geq XX.5 will be rounded up to XX + 1 while values < XX.5 will be rounded down to XX.

Percentages will be based on available data and denominators will generally exclude missing values. For frequency counts of categorical variables, categories whose counts are zero will be displayed for the sake of completeness. For example, if none of the patients discontinue due to “lost to follow-up,” this reason will be included in the table with a count of 0. Categories with zero counts will not have zero percentages displayed.

Unless otherwise specified, percentages will be calculated based on the number of patients specified by the appropriate population definition.

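### SAP 13.8 and 13.9 divide renal outcomes that are seen only when measured by all time on therapy: incidence is diluted by an amount that depends on period length, and the prevalence denominator is ambiguous

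*SAP*

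**What the plan says.** SAP 13.8 (rapid decline in mGFR or eGFR) and 13.9 (micro- or macroalbuminuria) are secondary endpoints for comparing migalastat, ERT and untreated patients. Neither section defines a denominator. Each states that the endpoint "will be analyzed using same methodology as for incidence and prevalence of FACEs".

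The borrowed rules are these:

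- **Prevalence (SAP 13.2):** "calculated as a ratio of patients with at least one FACE on a given therapy divided by the number of patients on that therapy".
- **Incidence (SAP 13.3):** a rate per 1000 person-years, over time from the Analysis Start Date or switch date on each therapy and over untreated periods. The numerator is given in two ways: "The analysis of the incidence rate (number of patients with at least 1 event per 1000 person-years", and later "The calculation of the incidence rate (number of events per 1000 person-years".

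Neither rule requires a measurement, ends person-time at the last measurement, or removes patients who already meet the criterion at the start of the period.

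Three other places bear on the point:

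- **SAP 7.1** says "Percentages will be based on available data and denominators will generally exclude missing values". It also says that, unless otherwise specified, "percentages will be calculated based on the number of patients specified by the appropriate population definition".
- **SAP 6.2** drops a patient with no usable laboratory value from the analysis of that variable at that time point. It does not mention person-time.
- **SAP 2** says that patients "have been offered annual or biannual thorough workups". The Protocol (Method) gives the interval as yearly or every other year.

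**The concern.** A stroke or the start of dialysis has a date of its own and normally enters the record when it happens. Time on therapy is then a reasonable denominator. Albuminuria and GFR decline have no such date. They come to light only at a sample, and a decline that must be sustained needs more than one later sample.

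If the denominator is all time on therapy, two kinds of time are counted as event-free although no event could have been seen: the stretch after the last measurement in a period, and the whole period of a patient never measured in it. The inclusion criteria do not prevent this. They ask for a baseline visit and one follow-up visit per patient, not per treatment period or per laboratory variable.

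The unmeasured stretch at the end of a period depends on the visit interval, not on the period's length, so it is a larger share of a short period. Groups with different period lengths are then diluted differently, and a rate ratio can move away from 1 with no true difference. SAP 3.2 tests these comparisons at the two-sided 0.05 level without multiplicity adjustment.

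**Working it through.** The documents state no rate, event count, period length or missing share for these endpoints, so there is no figure of theirs to reproduce. What follows is illustration.

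**Inputs from the documents.** Measurement every 1 or 2 years (Protocol, Method). Migalastat available from 2016 (Protocol, Rationale and background). Follow-up ends in December 2022 (Protocol) or December 2023 (SAP 2). A migalastat period can therefore last at most about 7 or 8 years, while follow-up from 2001 allows other periods of more than 20 years.

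**Assumed inputs.** True onset hazard 0.05 per year in both groups; a value at period start and then every *v* years; no extra value at period end; migalastat periods uniform on 0.5–7 years, untreated on 0.5–20 years; one qualifying value shows the event.

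**Hand check.** The unmeasured tail averages about *v*/2 per period, so the measured share is about 1 − (*v*/2)/mean length. Mean lengths are (0.5+7)/2 = 3.75 and (0.5+20)/2 = 10.25 years.

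- Yearly: 1 − 0.5/3.75 = 0.87 and 1 − 0.5/10.25 = 0.95; ratio 0.91.
- Two-yearly: 1 − 1/3.75 = 0.73 and 1 − 1/10.25 = 0.90; ratio 0.81.

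**Simulation** (4,000,000 periods per group). The rate is detected events divided by time to detection or period end (as 13.3 reads), or by time to detection or last measurement (the fix), per 1000 person-years.

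| Measurement | Denominator | Migalastat | Untreated | Ratio |
|---|---|---|---|---|
| Yearly | all therapy time | 42.4 | 46.7 | 0.91 |
| Yearly | measured time | 48.8 | 48.7 | 1.00 |
| Two-yearly | all therapy time | 35.8 | 43.6 | 0.82 |
| Two-yearly | measured time | 47.7 | 47.7 | 1.00 |

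Measured-time rates lie slightly below the true 50 because onset is dated at detection. This affects both groups alike.

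**Sensitivity to the assumptions** (yearly, two-yearly):

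- Untreated periods 0.5–7 years: 1.00, 1.00.
- Untreated periods 0.5–5 years: 42.4/39.9 = 1.06 and 35.8/31.2 = 1.15. The direction reverses.
- Untreated periods 0.5–20 years, half of all periods ending with a measurement: 0.96, 0.92. If every period does: 1.00.

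**Sustained GFR decline.** Assume that two consecutive values are needed and that the first measurement falls at a random point within the first interval. Reported/true for a 5-year period is 0.70 (yearly) or 0.41 (two-yearly), against 0.94 or 0.87 for 22 years. With one value the same set-up gives 0.89 or 0.78, against 0.96 or 0.93.

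**Never-measured patients.** If they supply 10% of the person-time, the rate falls by 10%. For prevalence, reported = measured share × true prevalence: a true 40% becomes 36%, 32% or 28% when 90%, 80% or 70% are measured. With equal true prevalence, the migalastat/comparator ratio is 0.70/0.90 = 0.78, 0.80/0.80 = 1.00 or 0.90/0.70 = 1.29, depending on who is measured more.

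**Patients already positive at baseline.** Let a share *q* be positive, with hazard 0.05 over 5 years, and a = 1 − exp(−0.25) = 0.221.

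- Counted as events: (q + (1−q)a) / ((1−q)a/0.05), which is 75 per 1000 person-years for q = 0.1 and 147 for q = 0.3.
- Kept in the denominator only: (1−q)a / ((1−q)a/0.05 + 5q), which is 44 and 34.

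**The case against.** A reader might infer that the reported rates are bound to be too low, and most so for migalastat. The documents do not support that.

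- **Direction between groups.** Availability from 2016 caps migalastat periods but does not make them the shortest. Untreated time ends when therapy starts and includes gaps after switches, and ERT periods ended by a switch may also be short. No period lengths or measurement frequencies by group are given.
- **Overall level.** Patients already albuminuric at baseline are not removed. If counted as events, they push the rate up by more than the dilution lowers it.
- **Closing measurements.** SAP 6.2 treats treatment-switch dates as required laboratory time points. Periods that end in a switch may have a closing value, which shrinks the effect. Periods that end at data cut-off need not.

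A reader might also infer that unmeasured patients certainly enter the prevalence denominator. SAP 6.2 and the first convention in 7.1 point to leaving them out; 13.2 and the population-size default in 7.1 point to keeping them. That is ambiguity, not a settled error. Nor does the SAP's rule on covariates with more than 50% missing say anything about missing albuminuria or GFR outcomes; it concerns model covariates.

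Two further objections carry some weight. The FACE definition itself contains a measured component, doubling of creatinine on two consecutive values, so the contrast with FACEs is not absolute. That extends the problem and does not defend the method. And precision is poor: assuming 30–40 migalastat and 40–60 untreated patients, a rate ratio would have a 95% interval of about 0.4 to 2.5, wide beside a 9–18% shift. The shift is systematic, however, and costs little to remove.

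What no passage answers is the incidence denominator. The conventions in 7.1 concern percentages, and 6.2 concerns single time points.

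**Conclusion.** The point holds for incidence as a defect of the stated method. Followed as written, 13.8 and 13.9 count time in which no event could be seen as event-free. This dilutes the rate, more in shorter periods, so the between-group ratio partly reflects period length and measurement frequency.

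The cap of about 7–8 years makes a bias in favour of migalastat possible. Its size (0.91 or 0.82 here) rests entirely on the assumed hazard, period lengths and absence of closing measurements, and its sign can change. The dilution is larger for GFR decline if two values are needed to show that it is sustained.

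For prevalence, the finding is narrower: "divided by the number of patients on that therapy" in 13.2 conflicts with the missing-value convention in 7.1, and two programmers could reasonably produce different results. The wording should be settled before the analysis is programmed.

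**What to change.** In SAP 13.8 and 13.9, replace the reference to the FACE method with explicit rules:

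- **At risk for incidence:** patients with a baseline value in the treatment period who do not already meet the criterion and who have enough later values in that period to show the event. That means at least one for albuminuria, and enough to confirm a sustained decline for GFR. State how *sustained* is operationalised.
- **Person-time:** from that baseline measurement to the first qualifying value (for GFR, the confirmed one) or the last evaluable measurement in the period.
- **Prevalence denominator:** patients with at least one evaluable measurement on that therapy.
- **Reporting:** the number of patients measured, by treatment group, beside each rate.

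The cost is SAP wording and programming; no new data are needed. The downside is smaller denominators and slightly wider intervals.
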